15.0 Statistical Considerations

Descriptive statistics will be used to summarize subject characteristics, for example subject demographics (age and gender, race, ethnicity, income, current occupation and usual occupation), medical history and current health status for current diagnoses, symptoms and past health problems. Categorical variables will be described by their frequencies and the continuous measurements will be described by their mean, median, range, and standard deviations. We will use paired *t*-test to compare distributions of continuous variables (e.g., age, number of cigarettes per day, number of pack-years of cigarettes smoked over lifetime) between the two treatment groups (watercress and placebo arms). The McNemar's Chi-squared test will be used to compare categorical variables, such as sex, *GSTM1* and *GSTT1* genotypes between the two treatment groups.

The statistical analysis section particularly focuses on Specific Aim 3, which investigates the hypothesis that detoxification of these noxious agents by conjugation with glutathione, as indicated by mercapturic acid levels in urine, will be significantly elevated compared to placebo in subjects who consumed the watercress preparation and are null for *GSTM1*, *GSTT1*, or both. We can test for a Period x Treatment interaction such as testing if the effect of the watercress preparation varies depending on whether it is given in the first period compared to the second period.

PROTOCOL TITLE: Watercress in Detoxification of Environmental Toxicants and

Carcinogens

VERSION DATE: July 23, 2020

We will have baseline measurements on each subject. Participants will be asked to attend clinic visits on days 0 (baseline), 2, 7 and 14 for each of the periods they are receiving product (watercress or placebo). We will compare the baseline measurements on the outcome variables and some important covariates between the two treatment groups through the two-sample t test to see if there is any significant difference between the two groups in order to ensure homogeneous treatment groups. We will also perform repeated data analysis using the measurements on each subject and consider different baseline parameters for the watercress and the placebo group in our multivariate regression analysis described later.

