Measurements: For the comparison between the two treatment groups, we will consider measurements excluding the baseline observation. Measurements will be taken from each subject in the two supplementation sequences as seen in the following diagram:

Group 1: Period #1 (watercress; A1) – washout – Period #2 (placebo; B2)

Group 2: Period #1 (placebo; B1) – washout – Period #2 (watercress A2)

The letter is used to denote supplementation (A for watercress and B for placebo) and the number, 1 or 2, denotes the period. We will assume, in the formulation of statistical models, that the measurements A1, A2, B1, and B2 are “normally distributed” in log-scale. These letters can represent one of our outcome variables: urinary mercapturic acid levels of specific toxicants (e.g. benzene, acrolein, crotonaldehyde, propylene oxide, etc.) or for mercapturic acids generally, or DNA adducts of acrolein.

Main Outcome Variables: Our data analysis will be based on the following “outcome variables”:

$$X1 = B2 - A1; \text{ and } X2 = B1 - A2.$$

This subtraction will cancel the “within-sequence” effects of all subject-specific factors, leaving only two to be modeled and analyzed: the Treatment (or Supplementation) effect and the Period (or Order) effect. The measurements will result in two independent samples. Each will have the same sample size if there are no dropouts or missing data. Otherwise the number of subjects for each group of measurements (i.e., X1 and X2) will differ if there are dropouts and missing data.

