We would obtain values of X1 or X2, which is a log of "ratio" for each subject in each of the two groups with different supplementation order, it's (watercress/placebo) for group 1 and (placebo/watercress) for group 2. We'll then compute the averages of these log ratios, i.e \bar{x}_1 and \bar{x}_2 . We will do this calculation separately for the double null group ($\hat{\alpha}_{nn}$), and single null group ($\hat{\alpha}_{np}$). We will compare this average ratio with the average ratio of the double positive group ($\hat{\alpha}_{pp}$). With the double nulls being about 15% of the population, *GSTM1* single nulls (45%) and *GSTT1* single nulls (23%), we expect to see 60 double nulls, 180 *GSTM1* single nulls, 92 *GSTT1* single nulls, and 68 double positive individuals. If there is no influence of *GSTM1* or *GSTT1*, the effect of watercress supplementation would be the same between the double null and the double positive group or between the single null and the double positive group. We will test for the significance of the genotypic effect by using a two-sample t test.

PROTOCOL TITLE: Watercress in Detoxification of Environmental Toxicants and

Carcinogens

VERSION DATE: July 23, 2020

In order to estimate the power for that comparison, we need information on the variability of mercapturic acid levels within and between subjects. We will compute the variances of each of these genotypic groups separately and then obtain a pooled variance estimate to compute our pooled t test statistic. Based on our previous work, we used an intra-subject CV of 0.4 and an inter-subject CV of 0.6, which translates to a pooled standard deviation of 0.657. According to Table 3, the percentage difference between the Placebo and PEITC groups with the double null genotypes varied from 29.8% to 95.4%, whereas the percentage difference for the double positive genotypes varied from 4% to 7%. In general, we will have 80% power to detect a difference of 35% between the double null and double positive group and given the range of difference between these two groups in Table 3, we expect to have good power to study this interaction between watercress and *GSTM1* or *GSTT1* genotypes.

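### The plan's only power figure uses an SD that does not fit the within-person log difference being tested, and its general claim of good power does not follow from the plan's own inputs

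*Combined protocol and SAP*

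**What the plan says.** Section 15.0 defines the outcome as each person's difference in log measurement between the placebo and watercress periods. It says the subtraction cancels the "effects of all subject-specific factors, leaving only two to be modeled and analyzed", namely treatment and period. The mean log ratios of the genotype groups are then compared by a two-sample t test.

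For that comparison the section states: "we used an intra-subject CV of 0.4 and an inter-subject CV of 0.6, which translates to a pooled standard deviation of 0.657". It then says "we will have 80% power to detect a difference of 35% between the double null and double positive group" and, pointing to the range of effects in Table 3, "we expect to have good power to study this interaction between watercress" and genotype. No alpha or sidedness is given.

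The expected groups are 60 double nulls, 180 GSTM1 single nulls, 92 GSTT1 "single nulls, and 68 double positive individuals". These add to 400, the enrolment figure. Section 10.0 says 350 are needed and allows for 15% attrition.

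On visits, the section says that "we will consider measurements excluding the baseline observation" and lists "days 0 (baseline), 2, 7 and 14 for each of the periods they are receiving product". Section 5.0 has day 4 in place of day 2, but either way there are three post-baseline visits per period. How they form one value for the t test is not said.

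**The concern.** The inter-subject CV describes how levels differ between people. A within-person difference removes that variation, so an SD built from both CVs belongs to a different statistic.

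The 35% is compared with the percentages in Table 3, which are on a ratio scale, yet the text does not say whether 35% is a ratio, percentage points or log units. One of the three Table 3 contrasts falls below 35% on all of these scales, which sits badly with citing that table as evidence of good power.

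This is the plan's only power figure; the later remark on smokers gives no number. It supports the genotype hypothesis on which Section 15.0 says it focuses. If the acrolein or crotonaldehyde interaction is not significant, readers will judge that result against a power claim the plan has not shown.

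**Working it through.** **Inputs.** Intra-subject CV 0.4, inter-subject CV 0.6, SD 0.657 and genotype shares of 15% and 17% (60 and 68 of 400) are from Section 15.0. The figures of 350 needed and 15% attrition (400 × 0.85 = 340) are from Section 10.0. Effects and intervals are from Table 3, genotype counts from Table 2. Two-sided 5% is my assumption.

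**Formula.** SE = SD × √(1/n₁ + 1/n₂); power = Φ(δ/SE − 1.96), the opposite tail being negligible. An exact t calculation lowers the results by under one point.

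**The plan's SD.** The log-scale variances are ln(1 + 0.4²) = 0.1484 and ln(1 + 0.6²) = 0.3075. The usual combinations are:
- √(0.1484 + 0.3075) = 0.675
- √ln(1 + 0.16 + 0.36) = 0.647
- √(0.16 + 0.36) = 0.721

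None is 0.657, and its derivation is not shown. For a within-person difference:
- one sample per period: √(2 × 0.1484) = 0.545
- mean of three visits with independent errors (an assumption): √(2 × 0.1484/3) = 0.315

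Both assume that response does not vary between people.

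**The plan's 80%, at SD 0.657.** With 60 and 68, SE = 0.657 × 0.1771 = 0.1164. Then 0.35/0.1164 = 3.01, giving 85.3%, and ln 1.35/0.1164 = 0.300/0.1164 = 2.58, giving 73.2%.

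| Reading of 35% | N = 400 | 350 | 340 |
|---|---|---|---|
| 0.35 log units (ratio 1.42) | 85.3% | 80.3% | 79.2% |
| Ratio 1.35 | 73.2% | 67.5% | 66.2% |
| Ratio 1.35, one-sided 5% | 82.5% | 77.9% | 76.8% |

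With the printed shares and two-sided 5%, 80% appears only for 0.35 log units and groups drawn from about 340–350 participants.

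**Table 3 contrasts, double null over double positive.**
- SPMA: 1.954/1.061 = 1.84 (log 0.611)
- 3-HPMA: 1.327/1.070 = 1.24 (log 0.215; 25.7 points)
- HMPMA: 1.298/0.960 = 1.35 (log 0.302; 33.8 points)

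**SDs implied by Table 3.** SD = [ln(upper ratio) − ln(lower ratio)]/3.92 × √n. Double null, double positive and pooled values are:
- SPMA: 0.581, 0.576, pooled 0.577
- 3-HPMA: 0.398, 0.437, pooled 0.428
- HMPMA: 0.322, 0.321, pooled 0.321

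**Power with the printed shares (N = 400 / 350 / 340).**

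| SD | 3-HPMA | HMPMA |
|---|---|---|
| 0.657 (plan) | 46 / 41 / 40% | 74 / 68 / 67% |
| 0.545 (one visit) | 61 / 55 / 54% | 88 / 83 / 82% |
| Table 3-implied (0.43; 0.32) | 81 / 76 / 74% | above 99% |
| 0.315 (three visits averaged) | 97 / 95 / 94% | above 99% |

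SPMA is above 99% throughout. HMPMA reaches 80% only if the SD is at most 0.61 / 0.57 / 0.56.

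**Genotype counts.** The plan's 45% and 23% for single nulls match the overall null frequencies in Table 2: 36/81 = 44% and 19/81 = 23%. Both of those include the 12 double nulls. Excluding them, Table 2 gives (36 − 12)/81 = 30% GSTM1-only and (19 − 12)/81 = 9% GSTT1-only, together 31/81 = 38%, with 38/81 = 47% double positive. The plan has (180 + 92)/400 = 68% and 68/400 = 17%. If 45% and 23% are overall frequencies, double positives are 1 − 0.45 − 0.23 + 0.15 = 47%, or 188 of 400. Power at SD 0.657 is then 60 / 54 / 53% for 3-HPMA and 87 / 82 / 81% for HMPMA. At SD 0.545, 3-HPMA has 76 / 70 / 69%; at 0.43 it has 92 / 89 / 88%.

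**Sign.** The plan says "the percentage difference for the double positive genotypes varied from 4% to 7" per cent. Table 3 gives −4.0% (HMPMA), 6.1% (SPMA) and 7.0% (3-HPMA).

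**The case against.** The strongest reply is that the SD error is on the safe side. Against 0.545 the plan understates its power, and at every alternative SD above HMPMA has at least 82% even on the printed counts. That stands: this is a fault in the power statement, with no evidence that the trial is too small.

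The two criticisms also interact. If double positives number 188, a ratio of 1.35 has 87 / 82 / 81% at the plan's own SD, so the 80% claim would then hold on the Table 3 scale and only 3-HPMA would stay below 80%. That also stands. The shortfall for HMPMA depends on the printed counts, and the genotype reading is an inference from 81 smokers, since the plan's four shares do add to 100%. The plan must say which counts it means.

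No replacement SD is secure either. Variation in response between people would raise 0.545 and 0.315, and the SPMA value of 0.58 already exceeds 0.545. The Table 3 values come from mixed-model intervals with only 12 double nulls, in smokers giving 24-hour urine on three days per period; this trial uses first-morning voids. If those intervals used t with 11 degrees of freedom, the double-null SDs would be 0.52, 0.35 and 0.29. For 3-HPMA double nulls, the interval implies P = 0.014, but the printed P of 0.034 implies SD ln(1.327)/2.12 × √12 = 0.46, at which power is 75 / 70 / 68% on the printed shares. This is why a range is needed.

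The supplementary mixed model handles repeated visits, but it leaves open how the t test, which is the analysis powered, combines them. The missing minus sign is minor, and restoring it favours the plan.

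**Conclusion.** The concern holds. The SD of 0.657 includes between-subject variance that the tested difference removes. The 80% cannot be reproduced from the printed 60 and 68 at two-sided 5%.

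At the plan's SD and shares, good power is supported for SPMA only. For 3-HPMA, power at SD 0.657 is 40–46% on the printed counts and 53–60% if double positives are 47%. HMPMA moves from 67–74% to 81–87% between those two sets of counts.

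These figures rest on two-sided 5%, the normal approximation and Table 3 effects carrying over to watercress. Table 3 gives no effect for the other five mercapturic acids in Table 1, so a general claim cannot rest on it for those. The conclusion is that power has not been shown, and it could prove good for all three biomarkers under a defensible SD.

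**What to change.** Settle the genotype counts first, by saying whether 45% and 23% are exclusive single-null shares or overall null frequencies, and correct the group sizes if needed. Then rewrite the power paragraph for the within-person log ratio:

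- State alpha, sidedness, the evaluable N and how the post-baseline visits form each period's value.
- Express the detectable effect as a ratio of ratios.
- Replace the general statement with separate power for SPMA, 3-HPMA and HMPMA over a range of SDs. The range could include 0.315, 0.545 and the Table 3-implied values (about 0.58, 0.43 and 0.32 respectively), with the assumptions behind each stated.
- Give the double-positive range as −4% to 7%.

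The cost is a recalculation and one paragraph of text. Enrolment does not change.

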1.0 Objectives

The goal of this proposal is to test the hypothesis that consumption of watercress, a rich source of the cancer chemopreventive agent 2-phenethyl isothiocyanate (PEITC), will enhance the detoxification of multiple environmental toxicants and carcinogens, particularly in subjects who are null for *glutathione-S-transferase M1 (GSTM1)*, *glutathione-S-transferase T1 (GSTT1)*, or both. If our hypothesis is supported by the results of the trial, watercress could emerge as an inexpensive and plentiful dietary constituent which could promote good health by decreasing the effects of environmental stressors.

We and others have carried out extensive studies on the efficacy and mechanisms of PEITC in the context of cancer chemoprevention [1-21]. Our studies focused on the potential use of PEITC in prevention of lung cancer in smokers, as we have demonstrated that PEITC is a powerful inhibitor of lung carcinogenesis in rats and mice treated with the tobacco-specific lung carcinogen 4-(methylnitrosamino)-1-(3-pyridyl)-1-butanone (NNK) [2,20]. These studies led to a clinical trial of PEITC with the goal of determining whether it could inhibit the metabolic activation of NNK, as observed in rats and mice [11]. The results of that trial demonstrated a modest but significant effect of PEITC in decreasing the metabolic activation of NNK in cigarette smokers [11].

Unexpectedly however, PEITC showed far greater effects on the detoxification of benzene, acrolein, and crotonaldehyde in subjects who were null for *GSTM1*, *GSTT1*, or both [21] (see Preliminary Results). We now wish to extend these exciting results and assess the effects of watercress, as an abundant source of PEITC as well as other isothiocyanates, on the detoxification of environmental toxicants and carcinogens in a trial that will recruit *both* non-smokers and smokers in proportion to their prevalence in the Minnesota population. All humans are exposed to benzene, acrolein, crotonaldehyde and other related toxicants and carcinogens through their diet, polluted air, and/or endogenous metabolic sources.

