10.0 Local Number of Participants

Three hundred and fifty participants are needed for the study. Anticipating a 15% attrition rate, a total of 400 of participants will be enrolled into the study. We expect about 300 non-smokers and about 100 smokers.

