We will also perform the above analysis separately for smokers and non-smokers. We expect to see about 25% smokers (~ 100 smokers) in our sample. We might have limited power to detect the impact of watercress for the double-nulls among the smokers, however this subgroup analysis would reveal if there are suggestive differences in the association of urinary mercapturic acid levels, watercress and *GSTM1*, *GSTT1* between the smokers and the non-smokers.

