Multivariate Regression Analysis: We will use multivariate regression analysis to supplement the t-test by pooling the data together and using each of the primary outcome variables as dependent variable, separately. In addition to the variables representing the supplementation, treatment order, and status of *GST (M1, T1)* genotypes, the list of independent variables will include socio-demographic characteristics such as gender, age, smoker vs non-smoker, baseline smoking level (cigarettes per day), and intake of dietary nutrients. We will fit a linear mixed-effect model where the dependency in the repeated measurements on each individual will be captured through a random effect. The status of *GST (M1, T1)* genotypes will be modeled as fixed-effects and we will test for the null hypothesis of no association between the genotypes and each outcome. Our primary parameter of interest will be the interaction between the treatment order (pre vs post) and the genotype groups (double null, *GSTM1* single null, *GSTT1* single null, and double positives). We will perform a t-test to assess the significance of the interaction parameter. The residual covariance structure should be selected among several candidates, i.e. autoregressive, compound symmetry, unstructured, etc., to estimate the fixed and random effects. We do not anticipate much missing data on the participants. In general, we will assume missingness at random (MAR) and the likelihood-based linear mixed effect model will provide consistent estimates of our parameters of interest in presence of MAR. The models will be assessed through their Akaike's Information Criterion and Bayesian's Information Criterion. The normality of the outcome variables will be assessed and in presence of non-normality, we will also implement Generalized Estimating Equations to study the impact of watercress and genotypes on each outcome variable. We will use the statistical software R packages nlm and gee to perform the above analysis. These packages will also provide the flexibility to fit non-linear mixed effect models to assess the impact of watercress and genotype groups.

PROTOCOL TITLE: Watercress in Detoxification of Environmental Toxicants and Carcinogens

VERSION DATE: July 23, 2020

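### The smoker and non-smoker comparison rests on separate genotype t-tests; section 15.0 names no smoking interaction and no between-group estimate

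*Combined protocol and SAP*

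**What the plan says.** Section 15.0 sets out a two-sample t-test of the watercress log ratio between genotype groups, then adds: "We will also perform the above analysis separately for smokers and non-smokers". On numbers it says "We expect to see about 25% smokers (~ 100 smokers) in our sample", and section 10.0 agrees: "We expect about 300 non-smokers and about 100 smokers". It gives a caution, "We might have limited power to detect the impact of watercress for the double-nulls among the smokers", but goes on to say that "this subgroup analysis would reveal if there are suggestive differences in the association of urinary mercapturic acid levels", watercress and the two genes between smokers and non-smokers.

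The multivariate regression part of section 15.0 includes smoking in its list of independent variables: "smoker vs non-smoker, baseline smoking level (cigarettes per day"). The interaction it names as the parameter of interest is between treatment order and genotype. Section 15.0 also mentions a period by treatment interaction. It names no interaction that involves smoking.

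Section 1.0 describes extending the earlier results, which section 2.0 shows came from smokers only, to a trial that recruits both "non-smokers and smokers in proportion to their prevalence in the Minnesota population".

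**The concern.** The subgroup paragraph promises information about a difference between two groups, but the analysis it specifies looks at each group alone. Two separate tests do not test a difference. When one group is three times the size of the other, the same true effect can easily be significant in the larger and not in the smaller.

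The regression as described does not fill the gap. A main effect of smoking moves a person's watercress and placebo values by the same amount. It therefore drops out of the within-person contrast and does not show whether the watercress effect, or its dependence on genotype, differs by smoking.

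At stake is how the trial reports whether a result first seen in smokers looks different in non-smokers. With no between-group estimate called for, a reader may fall back on comparing two P values.

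**Working it through.** **Inputs from the plan**
- Section 10.0: 400 enrolled, 350 needed, about 100 smokers and 300 non-smokers.
- Section 15.0: 60 double nulls and 68 double positives among 400; SD 0.657 on the log scale; 80% power for a 35% difference between these two genotype groups.
- Table 3: percentage effects by genotype in the earlier PEITC trial.

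**Assumptions**
- Two-sided 5% (section 15.0 states no level), genotype independent of smoking, and equal SD in smokers and non-smokers.
- The cells at 400 are then 15 v 17 (smokers) and 45 v 51 (non-smokers). At 350 each is multiplied by 0.875.

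**Step 1. Reproduce the plan's 80%.** At 350 the groups are 52.5 v 59.5. SE = 0.657 × √(1/52.5 + 1/59.5) = 0.124. Reading 35% as 0.35 log units, 0.35/0.124 = 2.81, and power = Φ(2.81 − 1.96) = 80%. The stated figure reproduces. Reading 35% as ln(1.35) = 0.300 gives 67% at 350 and 73% at 400. Both readings are carried forward.

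**Step 2. The plan as written, with the same true genotype effect in both smoking groups.** Power is from the noncentral t with noncentrality d / [SD × √(1/n₁ + 1/n₂)]. With powers p₁ and p₂, exactly one group is significant with probability p₁(1 − p₂) + p₂(1 − p₁).

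| Cells | Effect d | Smokers | Non-smokers | Only one significant |
|---|---|---|---|---|
| 400 | 0.35 | 31% | 73% | 59% |
| 400 | ln(1.35) | 24% | 60% | 55% |
| 350 | 0.35 | 27% | 67% | 58% |
| 350 | ln(1.35) | 21% | 54% | 52% |

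Example, second row: 0.599 × 0.761 + 0.239 × 0.401 = 0.456 + 0.096 = 0.55. The 0.456 is the non-smokers-only pattern. Simulating 20,000 trials for the first row gave 59.5%, and a genotype by smoking interaction test called a difference in 5.2% of them.

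**Step 3. How far the figure moves (cells at 400 unless stated).**
- SPMA contrast from Table 3, ln(1.954/1.061) = 0.611: 28% at SD 0.657 (35% at 350). At SD 0.545, which is √(2 × ln(1 + 0.4²)) for a difference of two single log measurements at the plan's intra-subject CV, it is 14%.
- 3-HPMA, ln(1.327/1.070) = 0.215: 40% at SD 0.657.
- HMPMA, ln(1.298/0.960) = 0.302: 55% at SD 0.657.
- If three post-baseline visits with independent errors are averaged, SD = 0.545/√3 = 0.315. The 35% effect then gives 14% (0.35) to 26% (ln 1.35), or 19% to about 33% at 350. For SPMA it is near zero.
- Table 2 has 38/81 = 47% double positives, against the 17% (68/400) in section 15.0. With 47%, the 35% effect at SD 0.657 gives 56 to 59%, so the result does not depend on that count.

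**Step 4. What an interaction could detect at SD 0.657.**
- Supplementation by smoking, 100 v 300: SE = 0.657 × √(1/100 + 1/300) = 0.076. The difference detectable with 80% power is 2.80 × 0.076 = 0.213, a ratio of 1.24 (1.26 at 350). Power is 83% (77% at 350) for a gap of 24.6%, the size of the whole earlier SPMA effect. For a gap of 15.1%, the size of the earlier 3-HPMA effect, it is 46% (41% at 350).
- Supplementation by genotype by smoking: SE = 0.657 × √(1/15 + 1/17 + 1/45 + 1/51) = 0.27. The 95% CI factor is exp(1.96 × 0.27) ≈ 1.7 and the detectable ratio is exp(2.80 × 0.269) ≈ 2.1.

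**The case against.** The plan is more cautious than a quick reading suggests. It speaks only of suggestive differences, admits limited power among smoker double nulls, and sets no rule for declaring that the groups differ. The underlying analysis yields average log ratios as well as P values, so a reader could subtract one group's genotype contrast from the other's and attach a CI. Section 1.0 puts its hypothesis on watercress and GST genotype and predicts no difference by smoking. Carrying the earlier result over to non-smokers needs an estimate in non-smokers, and the separate analysis supplies one for the genotype contrast.

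Much of this stands, and it rules out three stronger readings that a reader might infer:
- That the trial will announce an effect in non-smokers only. No decision rule says so; the one-group-only figures apply only if significance results are compared.
- That the plan leaves a well-powered smoking question untested. Power is good only for a gap about as large as the whole earlier SPMA effect. A gap of 15% would be missed more often than found.
- That both groups were recruited in order to test a smoking difference. The documents do not say this.

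What remains is that the text offers a between-group conclusion without asking for the between-group estimate. Admitting low power in one group does not help, because unequal power is what produces a spurious contrast.

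**Conclusion.** The point holds as a defect in a secondary analysis. Section 15.0 bases a smoker v non-smoker comparison on separate tests and names no between-group test or estimate; the smoking covariate does not supply one. If significance results are compared, an identical 35% genotype effect looks like a difference in about 52 to 59% of trials at SD 0.657, against 5% with an interaction test. The rate is lower for a larger contrast or a smaller SD: 28% for SPMA and 40% for 3-HPMA at SD 0.657, 14% for SPMA at SD 0.545, and 14 to 26% for the 35% effect at SD 0.315. All of this rests on the assumptions listed with the inputs. An interaction test corrects the false-difference rate, but it does not make the genotype by smoking question answerable at this sample size.

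**What to change.** In the subgroup paragraph of section 15.0, base any comparison of smokers with non-smokers on one pooled model:
- Add supplementation by smoking status, test it in all participants, and state its limited power for modest gaps.
- Add supplementation by genotype by smoking, and report it only as an estimate with a 95% CI, labelled exploratory.
- Take the smoker and non-smoker effects from this same model.
- State that a difference between the groups will be claimed only from the interaction term, not from the separate P values.

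The cost is a few sentences, two model terms and one secondary test that may miss modest differences. No new data are needed.
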